8.1 Discontinuation Criteria of Nivolumab

Nivolumab administration should be discontinued for the following:

- Any Grade \geq 2 drug-related uveitis, eye pain, or blurred vision that does not respond to topical therapy and does not improve to Grade 1 severity within the re-treatment period OR requires systemic treatment
- Any Grade 3 non-skin, drug-related adverse event lasting > 7 days, with the following exceptions for laboratory abnormalities, drug-related bronchospasm, hypersensitivity reactions, and infusion reactions:
 - Grade 3 drug-related laboratory abnormalities do not require treatment discontinuation except:
 - Grade 3 drug-related thrombocytopenia > 7 days or associated with bleeding requires discontinuation.
 - Any drug-related liver function test (LFT) abnormality that meets the following criteria require discontinuation:
 - Aspartate aminotransferase (AST) or alanine aminotransferase (ALT) $> 5-10x$ upper limit of normal (ULN) for > 2 weeks
 - AST or ALT $> 10x$ ULN
 - Total bilirubin $> 5x$ ULN
 - Concurrent AST or ALT $> 3x$ ULN and total bilirubin $> 2x$ ULN
 - Grade 3 drug-related bronchospasm, hypersensitivity reaction, or infusion reaction of any duration requires discontinuation

Proprietary of MD Anderson Cancer Center

- Any Grade 4 drug-related adverse event or laboratory abnormality, except for the following events which do not require discontinuation:
 - Grade 4 neutropenia \leq 7 days
 - Grade 4 lymphopenia or leukopenia
 - Isolated Grade 4 electrolyte imbalances/abnormalities that are not associated with clinical sequelae and are corrected with supplementation/appropriate management within 72 hours of their onset.
 - Grade 4 amylase or lipase abnormalities that are not associated with symptoms or clinical manifestations of pancreatitis. It is recommended to consult with the PI for Grade 4 amylase or lipase abnormalities.
- Any dosing interruption lasting $>$ 4 weeks with the following exceptions:
 - Dosing interruptions to allow for prolonged steroid tapers to manage drug-related adverse events are allowed. Prior to re-initiating treatment in a subject with a dosing interruption lasting $>$ 4 weeks, the Principal Investigator must be consulted. Tumor assessments should continue as per protocol even if dosing is interrupted.
 - Dosing interruptions $>$ 4 weeks that occur for non-drug-related reasons may be allowed if approved by the Principal Investigator. Prior to re-initiating treatment in a subject with a dosing interruption lasting $>$ 4 weeks, the UTMDACC IND Office must be notified. Tumor assessments should continue as per protocol even if dosing is interrupted.
- Any adverse event, laboratory abnormality, or intercurrent illness which, in the judgment of the Investigator, presents a substantial clinical risk to the subject with continued nivolumab dosing.
- Any Grade 3 drug-related laboratory abnormality, with the following exceptions for asymptomatic amylase or lipase, AST, ALT, or total bilirubin: Grade 3 amylase or lipase abnormalities that are not associated with symptoms or clinical manifestations of pancreatitis do not require a dose delay. It is recommended to consult with the PI for Grade 3 amylase or lipase abnormalities.
- Any Grade 3 colitis, neurologic toxicity, symptomatic pancreatitis, or pneumonitis.
- Any Grade \geq 3 Stevens-Johnson Syndrome or Toxic Epidermal Necrolysis (TEN).

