- Patients experiencing Grade 3 fatigue for > 5 days despite optimal supportive care should be taken off study with discontinuation of the combination therapy.
- In patients experiencing Grade 3 rash or Grade 2/3 diarrhea, both oral MGCD516 and nivolumab should be held until improvement to Grade ≤ 1 . Topical and/or systemic steroids can be given as needed. If no improvement to \leq Grade 1 after combination treatment has been held for > 3 weeks then the patient should be taken off study. Dosing interruptions for prolonged steroid tapers > 6 weeks to manage drug-related adverse events are allowed. The Principal Investigator must be consulted prior to re-initiating treatment in a patient with a dosing interruption lasting > 4 weeks.
- Patients experiencing Grade 3/4 elevation in serum amylase and/or lipase levels associated with clinical or radiological evidence of pancreatitis, with no other alternate etiology, should be taken off study with discontinuation of the combination therapy.

Discontinuation criteria for nivolumab and MGCD516 are described in sections 8.1 and 8.2, respectively.

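### Sections 8.1 and 6.4 give opposite nivolumab outcomes for drug-related Grade 3 diarrhea that stays at Grade 3 beyond 7 days but recovers within the 3-week hold

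*Combined protocol and SAP*

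**What the plan says.** Section 8.1 opens its list with "Nivolumab administration should be discontinued for the following". One entry is "Any Grade 3 non-skin, drug-related adverse event lasting > 7 days, with the following exceptions for laboratory abnormalities"; the exceptions also take in bronchospasm, hypersensitivity and reactions to the infusion. Diarrhea does not appear among them. A separate entry in the same list covers Grade 3 colitis and sets no minimum duration.

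Section 6.4 deals with diarrhea by name, among the overlapping toxicities of the two drugs: "In patients experiencing Grade 3 rash or Grade 2/3 diarrhea, both oral MGCD516 and nivolumab should be held until improvement" to Grade 1 or less. If that improvement has not come "after combination treatment has been held for > 3 weeks then the patient should be taken off study". The same bullet states that "Dosing interruptions for prolonged steroid tapers > 6 weeks to manage drug-related adverse events are allowed" and requires the Principal Investigator to be consulted before treatment is restarted after more than 4 weeks. It therefore contemplates restarting. It sets no 7-day limit for Grade 3.

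Section 6.4 ends with "Discontinuation criteria for nivolumab and MGCD516 are described in sections 8.1 and 8.2, respectively". Neither section says which prevails for diarrhea.

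**The concern.** One clinical course can meet both rules, and they lead to different places. Section 8.1 stops nivolumab. Section 6.4 pauses it and, on recovery, lets it start again. Sections 6.4 and 8.0 both allow one agent to continue when the other is stopped, so the rule applied decides whether a recovered patient goes back to the combination or continues on MGCD516 alone.

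The event is foreseeable. Section 5.3 names diarrhea first among the overlapping toxicities. Section 3.1.3.1 reports Grade 3 diarrhea with MGCD516, including one of the two SUSARs. Section 3.2.3.1 gives nivolumab-related diarrhea in 13.4% of patients in CA209003, with 1% at Grade 3/4.

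At stake are re-exposure to nivolumab after a severe gastrointestinal event and the consistency of the treatment whose ORR, PFS and OS the trial reports. Section 3.4 uses ORR and PFS for both historical and between-dose comparisons.

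**Working it through.** No plan figure has to be reproduced. The check sets the two rules side by side and applies them to the courses a patient might follow.

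**Inputs**
- Section 8.1: Grade 3, non-skin, drug-related, more than 7 days, so from day 8 at Grade 3. Consequence: discontinue nivolumab.
- Section 6.4, diarrhea bullet: Grade 2 or 3. Hold both drugs until Grade 1 or less. Off study if this is not reached after more than 3 weeks of holding, that is, more than 3 × 7 = 21 days.

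**The clocks.** Section 8.1 counts days spent at Grade 3. Section 6.4 counts time on hold until Grade 1 or less. If the hold starts on the first day of Grade 3, the rules diverge from day 8 to day 21. If the hold starts *d* days later, the upper end moves to day 21 + *d*. If it was already running for Grade 2 diarrhea, the upper end comes sooner.

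**Courses compared** (the first two timelines are illustrative)

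| Course of drug-related diarrhea | Section 8.1 | Section 6.4 bullet | Conflict? |
|---|---|---|---|
| Grade 3 for 10 days, then Grade 1 or less, hold not over 21 days | 10 > 7: discontinue nivolumab | Hold ends, nivolumab may resume | Yes |
| Grade 3 for 5 days, Grade 2 for 10 days, then Grade 1 or less (5 + 10 = 15 days) | 5 is not > 7: not triggered | Hold ends, nivolumab may resume | No |
| Grade 2 throughout | Not triggered | Hold and 3-week limit apply | No |
| Grade 3 over 7 days, not at Grade 1 or less after more than 21 days on hold | Discontinue nivolumab | Off study | No lasting difference for nivolumab |
| Classed as Grade 3 colitis | Discontinued under a separate entry, any duration | Diarrhea bullet does not name colitis | Settled by the colitis entry |

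Rash shares the 6.4 bullet but does not collide with the 7-day entry, which is limited to non-skin events. The same sentence in 6.4 is therefore compatible with that entry for rash and not for diarrhea.

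**Dose-finding endpoint.** Under Section 5.3, Grade 3 diarrhea lasting more than 3 days despite supportive care is already a DLT if judged clinically relevant and related. That threshold is passed before day 8, so which nivolumab rule is followed afterwards seldom changes whether the patient counts as a DLT. The 6-week efficacy outcome could change only indirectly, through early nivolumab exposure.

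**The case against.** The best defence is that the sections have different jobs. Section 6.4 concerns modifications and interruptions, and its last line assigns discontinuation to 8.1 and 8.2. The rules can then be applied in sequence: hold both drugs at onset; stop nivolumab once Grade 3 has lasted more than 7 days; take the patient off study if recovery has not come after more than 3 weeks of holding. The consequences differ (stopping one agent, leaving the study), and the 3-week limit still has work to do for Grade 2 diarrhea and for Grade 3 that falls to Grade 2 within 7 days.

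This reading is coherent, and it reduces the conflict. It does not remove it. The bullet nowhere says that it is subject to 8.1. Nor does 6.4 keep to interruptions: it ends combination therapy for prolonged Grade 3 fatigue and for pancreatitis, and it sets its own off-study limit for diarrhea. A reader following the diarrhea rule has no cue that an earlier nivolumab stop applies. Section 6.4 also says, of immune-related events generally, that restarting nivolumab may be considered depending on severity.

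Three stronger inferences are tempting, and the documents do not support them.
- *Every Grade 3 diarrhea of 8 to 21 days is affected.* The clocks differ, relatedness is required, and colitis is handled separately.
- *Each affected patient moves the adverse-event discontinuation rate by 1/42 = 2.4 points.* Section 3.4 reports 4/42 treatment discontinuations due to adverse events but does not say that stopping nivolumab alone counts. A patient continuing MGCD516 may not be in that numerator.
- *Safety depends on which section a local site happens to read.* Section 6.1.3 reserves study treatment decisions to the Principal Investigator or designee. The risk is inconsistency between decisions over time, not between sites.

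It also stands that both sections stop nivolumab dosing during the event, so the disagreement is about restarting after recovery. Section 8.1 further lets the investigator discontinue nivolumab for substantial clinical risk.

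**Conclusion.** The point holds as an internal inconsistency, limited to one course: drug-related diarrhea that stays at Grade 3 for more than 7 days, is not classed as Grade 3 colitis, and reaches Grade 1 or less before treatment has been held for more than 3 weeks. For that patient 8.1 discontinues nivolumab and the 6.4 bullet implies that it may resume.

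The number of such patients cannot be derived from the documents and may be zero. The effect falls on nivolumab rechallenge, later exposure to the combination, and the consistency of treatment behind ORR, PFS and OS. The effect on DLT counts is small. The conclusion assumes that discontinuation in 8.1 means stopping without restart, as distinct from a hold, and that the event meets 8.1's relatedness condition. It should be corrected because it touches re-exposure after a severe event and is easily put right. It does not undermine the dose-finding design.

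**What to change.** Reconcile the diarrhea bullet of Section 6.4 with the 7-day entry of Section 8.1, or state which prevails, so that one rule with one way of counting time applies to nivolumab. Which rule that should be is for the clinical team. The text change is one clause or cross-reference in an amendment.

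Section 3.4 reports 42 patients enrolled by February 2020 and 12 still on treatment at the September 2020 cutoff, so much of the value is now in reporting. List any patients whose Grade 3 diarrhea met the conditions above, with the rule followed and whether nivolumab was restarted. State also whether stopping nivolumab alone counts as an adverse-event discontinuation. This needs a review of existing adverse event and dosing records, and no new data collection.

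### Section 8.1 contradicts itself on stopping nivolumab for most kinds of Grade 3 drug-related laboratory abnormality; one bullet reads like a misplaced dose-delay rule

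*Combined protocol and SAP*

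**What the plan says.** Section 8.1 opens by saying that nivolumab should be stopped for each item that follows. Four parts of the list matter here.

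- One bullet stops nivolumab for "Any Grade 3 non-skin, drug-related adverse event lasting > 7 days" and allows exceptions, including one for laboratory abnormalities. Nested under it is the sub-rule: "Grade 3 drug-related laboratory abnormalities do not require treatment discontinuation except" for two groups. The first is "Grade 3 drug-related thrombocytopenia > 7 days or associated with bleeding requires discontinuation". The second is a set of AST, ALT and bilirubin thresholds.
- The Grade 4 bullet exempts four kinds of laboratory event: neutropenia of 7 days or less; "Grade 4 lymphopenia or leukopenia"; "Isolated Grade 4 electrolyte imbalances/abnormalities that are not associated with clinical sequelae", if corrected within 72 hours; and amylase or lipase changes without signs of pancreatitis.
- A later bullet lists as a reason to stop: "Any Grade 3 drug-related laboratory abnormality, with the following exceptions for asymptomatic amylase or lipase, AST, ALT, or total bilirubin". It then says that Grade 3 amylase or lipase changes without signs of pancreatitis need no delay in dosing, and recommends consulting the PI.
- A separate bullet covers "Any adverse event, laboratory abnormality, or intercurrent illness which, in the judgment of the Investigator, presents a substantial clinical risk to the subject" if dosing continues.

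Section 6.4 refers the reader to section 8.1 for the discontinuation criteria. It contains no separate list of laboratory criteria for holding nivolumab.

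**The concern.** A physician who sees, for example, a drug-related Grade 3 lymphopenia finds two answers in the same list: the sub-rule keeps the patient on nivolumab and the later bullet stops it. Section 10.1 requires a blood count and chemistry panel on Day 1 of each course in the main phase, so the question can arise at any cycle. Stopping an active drug for a value that the same section tolerates costs the patient treatment. Continuing departs from the letter of the later bullet. Nivolumab exposure, and any report of why nivolumab was stopped, then depends on which line was followed.

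**Working it through.** No figure in the plan needs reproducing. The check sets the two rules side by side for drug-related Grade 3 values and then looks for text that reconciles them.

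| Grade 3 drug-related value | Sub-rule | Later bullet | Result |
|---|---|---|---|
| Neutropenia, lymphopenia, leukopenia, anemia, electrolytes, other unlisted values | no stop | stop | conflict |
| Thrombocytopenia of 7 days or less, no bleeding | no stop | stop | conflict |
| Thrombocytopenia beyond 7 days, or with bleeding | stop | stop | agree |
| Asymptomatic amylase or lipase | no stop | exempt | agree |
| AST, ALT, total bilirubin | stop only at the listed thresholds | exempt | no conflict |

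**Does the nesting resolve it?** The sub-rule sits under the bullet on events beyond 7 days, so it might be read as an exemption from that bullet alone, with the later bullet standing as a separate criterion. Two consequences count against this reading.

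1. The later bullet would stop nivolumab for every drug-related Grade 3 thrombocytopenia, so the duration and bleeding conditions in "Grade 3 drug-related thrombocytopenia > 7 days or associated with bleeding requires discontinuation" would have no effect.
2. Nivolumab would stop at Grade 3 for values that do not stop it at Grade 4. Of the four Grade 4 laboratory exemptions, the later bullet repeats one at Grade 3 (asymptomatic amylase or lipase). Within the text of section 8.1 that leaves 4 − 1 = 3 inverted: short neutropenia, lymphopenia or leukopenia, and isolated corrected electrolytes. The electrolyte case is less clean, because section 6.4 separately takes patients with any Grade 4 non-hematological toxicity off study. The two hematologic inversions stand.

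**Does other text resolve it?** Sections 6.4, 8.0 and 8.1 do not say which rule governs. Section 6.1.3 gives treatment decisions to the PI or designee, and section 15.0 makes the PI the final arbiter of toxicity. Both settle who decides, not which rule applies.

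**What was probably meant?** The later bullet's explanatory sentence is about delaying a dose, which is out of place in a list of reasons to stop. The bullet also announces exceptions for AST, ALT and bilirubin but spells out terms only for amylase and lipase. Both features fit a dose-delay criterion placed in the wrong list. This is an inference from the wording; no other text confirms it.

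**Reach.** Section 3.4 reports 12/42 = 28.6% of patients still on trial treatment at the September 2020 cutoff. It describes 42 patients enrolled through February 2020 and gives final-style conclusions, so enrolment is taken as complete. The number reached after the cutoff is then between 0 and 12, because the number who entered the extension is not given. The practical reach is probably near the low end: in the extension, nivolumab follows standard of care (10.9), routine laboratory tests are at the physician's discretion (extension schedule) and routine adverse events are not collected (13.6). The 4/42 = 9.5% who stopped treatment for adverse events are not split by agent or by laboratory cause, so they say nothing about how often the conflict arose.

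**The case against.** The strongest reply is that there is no real contradiction of intent. If the later bullet is a hold rule, the sub-rule governs permanent stopping and the bullet governs delay. Holding a dose at Grade 3 is then compatible with not stopping permanently at Grade 4. As an account of intent this is persuasive, and it shapes the remedy. It does not rescue the text, because the bullet stands under a lead-in that says to stop.

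A second reply is that the disputed values may be rare. The Grade 3/4 drug-related laboratory events named in the background sections are serum amylase with MGCD516 (3.1.3.1) and AST/ALT at 0.3% each with nivolumab (3.2.3.1). AST/ALT and asymptomatic amylase are outside the conflict. This supports a low priority, but these are single-agent summaries and do not bound the rate for the combination.

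A third reply is that one institution directs all treatment decisions and that section 6.4 refers to the package insert for immune-related events. That reduces uneven handling but leaves the wording unresolved.

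On the other side, a reader might infer that patients were wrongly taken off nivolumab, or that dose selection was distorted. The documents support neither. No affected patient is identified. The DLT definition in section 5.3, which section 14.1 applies, does not depend on whether nivolumab was stopped under section 8.1. A reader might also conclude that the bullet should simply be deleted. That goes too far: deletion would lose the likely intended hold rule and the advice to consult the PI on Grade 3 amylase or lipase.

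**Conclusion.** Wrong as written; minor. For Grade 3 drug-related laboratory abnormalities other than asymptomatic amylase/lipase, AST, ALT and bilirubin, and other than thrombocytopenia that is prolonged or accompanied by bleeding, section 8.1 both says that no discontinuation is required and lists the value as a reason to discontinue. This conclusion needs only the text of the section. Two further statements rest on assumptions: that the bullet was meant as a dose-delay criterion (inferred from its wording), and that at most 12 of 42 patients could be reached after the cutoff (enrolment taken as complete). The effect is confined to nivolumab management and exposure. The DLT definition, the Lo-EffTox design and the stated design figures stand.

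**What to change.** Take the later bullet out of the section 8.1 list and restate it in section 6.4 as a nivolumab hold criterion for Grade 3 drug-related laboratory abnormalities. In doing so:

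- keep the exceptions for asymptomatic amylase/lipase, AST, ALT and total bilirubin, and the advice to consult the PI on amylase or lipase;
- exempt from the hold the values that section 8.1 exempts at Grade 4, so that Grade 3 is never handled more strictly than Grade 4;
- state that the limits on long interruptions (more than 4 weeks in section 8.1, more than 28 days in section 8.0) apply to these holds, and whether the section 8.1 allowance "Dosing interruptions to allow for prolonged steroid tapers to manage drug-related adverse events are allowed" can extend them.

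For laboratory values, the sub-rule with its thrombocytopenia and liver-test conditions, the Grade 4 bullet and the investigator-judgment bullet then govern permanent discontinuation. The cost is one short amendment to a safety instruction, with the usual review. No new data, assessments or analyses are needed.

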8.2 Discontinuation Criteria of MGCD516

General or specific changes in the patient's condition which render the patient unacceptable for further treatment in the judgment of the investigator. Patients may discontinue from study treatment or from the study at any time at their own request, or they may be discontinued at any time at the discretion of the investigator for safety, or behavioral reasons, or the inability of the patient to comply with the protocol required schedule of study visits or procedures at a given study site.

Criteria that may be used to discontinue patients from receipt of study medication will include, but will not be limited to:

- Objective disease progression according to RECIST 1.1 as determined by the investigator, (patients who may derive clinical benefit may continue on treatment at the discretion of the investigator);
- Global deterioration of health status requiring discontinuation;
- Adverse event;
- Significant protocol violation;
- Lost to follow-up;
- Refusal for further treatment;
- Study terminated by Sponsor;

- Death.

Reasons for discontinuation from study follow-up may include:

- Completed study follow-up;
- Study terminated by Sponsor;
- Lost to follow-up;
- Refusal for further follow-up for survival;
- Death.

If a patient does not return for a scheduled visit, every effort should be made to contact the patient. At least 2 attempts should be made to contact the patient and each attempt should be recorded in the source documents. In any circumstance, every effort should be made to document patient outcome, if possible. The investigator should inquire about the reason for withdrawal, request the patient to return for a final visit, and if applicable follow-up with the patient regarding any unresolved adverse events.

If the patient withdraws from the study treatment, and also withdraws consent for disclosure of future information, no further evaluations should be performed, and no additional data should be collected. The investigator may retain and continue to use any data collected before such refusal for further follow-up.

